### **7.4.4 Prior and concomitant therapy**

A prior or concomitant therapy is any drug or substance administered from 30 days prior to the screening visit through the final safety follow-up visit. For patients who are receiving breast milk, any drug or substance being administered to the mother during the period when she is breastfeeding will also be considered a concomitant medication. Maternal concomitant medications will also be collected, unless the breast milk is derived from a source other than the mother. Maternal concomitant medications will no longer be collected after the discontinuation of breastfeeding.

The patients/caregivers should be instructed that the patient not start taking any new medications, including nonprescription drugs and herbal preparations, unless they have received permission from the investigator.

#### **Allowed Concomitant Therapy**

Concomitant use of bypassing agents such as aPCC and rFVIIa will be allowed as described in Section 7.4.2.

Therapy considered necessary for the patient's welfare, including routine immunizations, may be given at the discretion of the investigator. Concomitant medications must be recorded in the CRF. Prescribed doses of FVIII bypassing agents will be documented in the CRF by the investigator while the patient/caregiver must enter actual dosing information on FVIII bypassing agents into the diary. AEs related to administration of these therapies must be documented in the CRF.

### **Disallowed Concomitant Therapy**

No other drug under investigation may be used concomitantly with the study treatment. Patients are not allowed to participate concurrently in another clinical study.

The following concomitant medications are not permitted through the end of treatment visit:

- Acetylsalicylic acid
- Current systemic treatment with chemotherapy and/or other immunosuppressant drugs. Use of corticosteroids for the treatment of asthma or management of acute allergic episodes is allowed with the exception of systemic corticosteroid treatment given to children daily or on alternate days at  $\geq 2$  mg/kg per day of prednisone or its equivalent or  $\geq 20$  mg/day if the duration is longer than 14 days.
- Concomitant immunomodulation will not be allowed during the study
- Concomitant emicizumab therapy will not be allowed during the study
- Any other FVIII product

Withdrawal due to use of disallowed concomitant therapy is described in Section 7.3.3.

Patients should be instructed to contact their investigators before taking any new medications, including nonprescription drugs and herbal preparations.

### **Concomitant Procedures**

A concomitant procedure is any therapeutic intervention (e.g., physical therapy) or diagnostic assessment (e.g., blood gas measurement, bacterial cultures) performed from 30 days prior to the screening visit until the final safety follow-up visit/telephone call. The diagnose for the therapeutic intervention will be recorded and the procedure described in the medical records and recorded in the CRF. AEs related to administration of these procedures must be documented on the appropriate CRF but not the procedure e.g. insertion of central venous access devices.

#### **7.4.5 Treatment compliance**

Prescribed dose and dosing frequency of rFVIIIFc will be documented in the CRF. The date and time of the rFVIIIFc administrations on Day 1 (Baseline) and the doses given in conjunction with study visits, which will be administered in the clinic, will be recorded in the CRF. The date, time, amount of and reason for rFVIIIFc administrations not done in conjunction with study visits will be recorded by the patient/caregiver in the diary.

Product accountability records will be kept. The pharmacy and the investigator must maintain accurate records demonstrating date and amount of packs received, to whom and by whom

administered or dispensed (patient -by- patient accounting), and accounts of returned packs and any packs accidentally or deliberately destroyed. All unused packs will be counted. Unless otherwise notified, the patient/caregiver should return all vials (used and unused) at each visit for full medication exchange and accountability. At the end of the study, any remaining packs will be returned to the CRO for destruction, or destroyed locally. In either case, a certificate of destruction must be issued.

## **7.5 Study assessments**

### **7.5.1 Study schedule**

### 7.5.1.1 Schedule of events

**Table 1** Schedule of events: Screening and ITI Period

Activities	Screening Visit - 4 weeks (- 2 weeks) from start of ITI treatment	ITI Period			
		Baseline Visit	Week 2 Visit	Interim ITI Visits	ITI Outcome Assessment Visit
		Start of ITI treatment	2 weeks ±3 days) from start of ITI treatment	Every 4 th week (±1 week ) starting at ITI Week 4 until negative titer (<0.6 BU/mL) is achieved OR 60 weeks of treatment	Every 4 th week (±1 week) starting at time of first negative inhibitor titer until IR>66% of expected is achieved OR until 60 weeks of treatment. Every 2 nd week (±3 days ) starting at time of first IR>66% until ITI success OR 60 weeks of treatment
Informed consent/assent	X				
Assessment of patient eligibility	X				
Demographics	X				
Medical, surgical, haemophilia, inhibitor, bleeding and ITI history	X				
Physical examination a	X	X		X	X
Height	X				
Weight (kg)	X	X	X	X	X
Vital signs b	X	X	X	X	X
Hematology a	X	X		X	X
Blood chemistry a	X	X		X	X
Urinalysis a	X	X		X	X
Viral analysis c	X				
Analysis of FVIII mutation d		X			

Activities	Screening Visit - 4 weeks (- 2 weeks) from start of ITI treatment	ITI Period			
		Baseline Visit	Week 2 Visit	Interim ITI Visits	ITI Outcome Assessment Visit
		Start of ITI treatment	2 weeks ±3 days) from start of ITI treatment	Every 4 th week (±1 week) starting at ITI Week 4 until negative titer (<0.6 BU/mL) is achieved OR 60 weeks of treatment	Every 4 th week (±1 week) starting at time of first negative inhibitor titer until IR>66% of expected is achieved OR until 60 weeks of treatment. Every 2 nd week (±3 days) starting at time of first IR>66% until ITI success OR 60 weeks of treatment
HLA allotyping d		X			
rFVIIIFc dosing e		X	X	X	X
Nijmegen-modified Bethesda assay (inhibitor assay)	X	X	X	X	X
Exploratory anti-FVIII antibody	X	X	X	X	X
Exploratory blood sample for immune cell characterization f		X	X		
FVIII:C g		X	X	X	X
FVIII:C for incremental recovery h					X
FVIII:C for half-life evaluation i					X
Diary review, including review of bleedings and rFVIIIFc dosing accountability j		X	X	X	X
Non-serious adverse events		X	X	X	X
Serious adverse events	X	X	X	X	X
Concomitant therapy/procedures	X	X	X	X	X

a Every 12th week from the start of the ITI treatment period.

b Vital signs include blood pressure, pulse rate, respiratory rate, and temperature. Postdose assessments following rFVIIIFc injections should be taken approximately 20 minutes after the end of the injection.

c Sample to be used to determine seropositivity, including anti-HIV-1 and -2, anti-HBs, and anti-HCV, at screening, should patients be diagnosed with HIV, hepatitis B, or hepatitis C, and results not already available in medical records.

d Not mandatory. To be collected at the baseline visit or at later visits unless results are available in medical records.

e Patients will be instructed that they will receive their daily dose of rFVIIIfc during the study visit after the samples for inhibitor testing and the FVIII:C pre-dose assessment are taken.

f A whole blood sample will be collected at the baseline visit (predose) and at Week 2, as allowable based on patient weight, regulatory guidelines and institutional practice regarding blood draw restrictions for pediatric patients.

g A pre-dose sample for FVIII:C will be collected at visits where samples for IR or t½ assessments are not collected.

h Assessment of incremental recovery will only be performed after negative inhibitor has been confirmed at two consecutive visits.

i Half-life determination will only be performed after incremental recovery >66% of the expected IR has been confirmed at two consecutive visits. Half-life determinations are to be performed after at least a 24-hour washout.

j It is recommended that patients/caregivers enter dosing information immediately after an injection.

**Table 2** Schedule of events: Tapering and follow-up period

Activities	Tapering period	Follow-up period		Final safety follow-up
	Tapering initiation visit, Week 2, 4, 8, 12 and 16 visits	Week 28 and 40 visits	End of treatment visita	Final safety follow-up visit
	Starting at ITI success and continuing for 16 weeks with visits after 2 weeks ( $\pm 3$ days), 4 weeks ( $\pm 1$ week) and then every 4 th week ( $\pm 1$ week)	Visits week 28 and 40 ( $\pm 2$ weeks) following ITI Success	Visit week 48 ( $\pm 2$ weeks) following ITI Success OR 2 weeks ( $\pm 3$ days) after failure or 60 weeks of treatment	7 to 14 days after the last dose of rFVIIIfc
Physical examination	X b	X	X	
Height			X	
Weight (kg)	X	X	X	
Vital signs c	X	X	X	

Activities	Tapering period	Follow-up period		Final safety follow-up
		Week 28 and 40 visits	End of treatment visit a	
	Tapering initiation visit, Week 2, 4, 8, 12 and 16 visits			Final safety follow-up visit
	Starting at ITI success and continuing for 16 weeks with visits after 2 weeks ( $\pm 3$ days), 4 weeks ( $\pm 1$ week) and then every 4 th week ( $\pm 1$ week)	Visits week 28 and 40 ( $\pm 2$ weeks) following ITI Success	Visit week 48 ( $\pm 2$ weeks) following ITI Success OR 2 weeks ( $\pm 3$ days) after failure or 60 weeks of treatment	7 to 14 days after the last dose of rFVIIIFc
Hematology d	X		X	
Blood chemistry d	X		X	
Urinalysis d	X		X	
rFVIIIFc dosing e	X	X	X	
Nijmegen-modified Bethesda assay (inhibitor assay) f	X	X	X	
Exploratory anti-FVIII antibody	X	X	X	
Exploratory blood sample for immune cell characterization g	X		X	
FVIII:C for incremental recovery	X	X	X	
FVIII:C for half-life evaluation h			X	

Activities	Tapering period	Follow-up period		Final safety follow-up
	Tapering initiation visit, Week 2, 4, 8, 12 and 16 visits	Week 28 and 40 visits	End of treatment visita	Final safety follow-up visit
	Starting at ITI success and continuing for 16 weeks with visits after 2 weeks ( $\pm 3$ days), 4 weeks ( $\pm 1$ week) and then every 4 th week ( $\pm 1$ week)	Visits week 28 and 40 ( $\pm 2$ weeks) following ITI Success	Visit week 48 ( $\pm 2$ weeks) following ITI Success OR 2 weeks ( $\pm 3$ days) after failure or 60 weeks of treatment	7 to 14 days after the last dose of rFVIIIFc
Diary review, including review of bleedings and rFVIIIFc dosing accountability j	X	X	X	
Non-serious adverse events	X	X	X	X
Serious adverse events	X	X	X	X
Concomitant therapy/ procedures recording	X	X	X	X

a Patients who do not achieve ITI success within 15 months will proceed to the end to treatment visit. Patients who develop inhibitors during the tapering or the follow-up period (i.e., who relapse) will proceed immediately to the end of treatment visit.

b Every 12th week during the tapering period.

c Vital signs include blood pressure, pulse rate, respiratory rate, and temperature. Postdose assessments following injections should be taken approximately 20 minutes after the end of the rFVIIIFc injection.

d During the tapering period, samples should be drawn every 12th week for testing.

e Patients will be instructed that they will receive their daily dose of rFVIIIFc during the study visit after the samples for inhibitor testing and the FVIII:C pre-dose assessment are taken.

- f An unscheduled visit may be required to repeat inhibitor testing under this protocol in order to obtain a sample to confirm a positive inhibitor test result.
- g If ITI success is declared, a sample will be collected at the first visit in the tapering period and at the end of the tapering period. If partial success or failure is declared a sample will be collected at the end of treatment visit.
- h PK assessments for half-life determination are to be performed in patients with a low or negative titer after at least a 24-hour washout.
- i It is recommended that patient/caregivers enter dosing information immediately after an injection.

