### 3                   **Ethics**

#### **3.1               Independent ethics committee**

It is the responsibility of the investigator to obtain approval of the study protocol, possible amendments and the written patient information and informed consent form (ICF) from the Independent Ethics Committee (IEC)/Institutional Review Board (IRB). The investigator should file all correspondence with the IEC/IRB. Copies of IEC/IRB correspondence and approvals should be forwarded to the contract research organization (CRO).

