#### Relapse

Relapse is defined as the occurrence of the following (with or without clinical signs or symptoms) after complete ITI success, based on the International ITI criteria [15]:

- A positive inhibitor ( $\geq 0.6$  BU using the Nijmegen assay) on 2 consecutive assessments, performed within 2-4 weeks

AND

- An IR  $\leq 66\%$  of the expected IR , on 2 consecutive assessments, performed within 2-4 weeks

If any assessments indicate relapse at any time during tapering or follow-up, the tests must be repeated at an unscheduled visit within 2 to 4 weeks to confirm relapse. A patient with confirmed relapse criteria will complete the end of treatment visit.

Throughout the tapering period all rFVIIIFc administration and any bleeding episodes will be registered by the patient and/or his caregiver in a study specific diary. The diary data will be reviewed by the investigator on an ongoing basis and discussed with the patient at each visit.

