#### **7.1.4 Follow-up period**

After completion of the tapering period, patients will enter the follow-up period. During the follow-up period patients will be treated prophylactically for up to 32 weeks with dose and frequency prescribed by the investigator, and according to the label and clinical response of the patient. If the tapering period has been prolonged, the follow-up period should be shortened accordingly but should not be less than 24 weeks.

During the follow-up period patients will visit the clinic every 12 weeks and undergo procedures and assessments as per the schedule of events (Table 2). At each visit, samples for inhibitor titer and IR assessments will be drawn to monitor for relapse. A patient with confirmed relapse criteria will complete the end of treatment visit.

In order to avoid bleeds and a relapse of the inhibitor titer, FVIII:C levels should be kept  $\geq 1$  IU/dL. Bleeding episodes during the follow-up period should be treated with rFVIIIFc, with doses according to investigator judgment and local practice. In specific situations, e.g. if bleeding is unresponsive to treatment with rFVIIIFc, treatment with bypassing agents may be considered as judged by the investigator. Such use is to be notified to the medical monitor and the rational documented in the medical records. Patients with bleedings during the follow-up period is to be tested for recurrence of inhibitors.

At the end of treatment visit, pharmacokinetic assessments to determine IR and half-life, if deemed measurable based on pre-dose FVIII:C, will be performed. Patients are required to have at least a 24-hour washout period prior to the half-life assessment.

Throughout the follow-up period rFVIIIFc administration and any bleeding episodes will be registered by the patient and/or his caregiver in a study-specific diary. The diary data will be reviewed by the investigator on an ongoing basis and discussed with the patient at each visit.

After the patient has completed the end of treatment visit, they should be treated and followed-up according to investigator judgment and local practice. No further investigational medicinal product will be provided.

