## Serious adverse event (SAE)

An adverse event that meets one or more of the following criteria/outcomes is classified as serious:

- Results in death.
- Is life-threatening (i.e., at immediate risk of death).
- Requires in-patient hospitalization or prolongation of existing hospitalization.
- Results in persistent or significant disability/incapacity.
- Is a congenital anomaly/birth defect (i.e., in an offspring to the study patient).

Other medically important adverse events that may not result in death, be life threatening, or require hospitalization may be considered serious when, based upon appropriate medical

judgment, they may jeopardize the patient or may require medical or surgical intervention to prevent one of the outcomes listed above. Examples of such events are intensive treatment in an emergency room or at home for allergic bronchospasm, blood dyscrasias or convulsions that do not result in hospitalization or development of dependency or abuse.

In this study, the following events are considered medically important and must be reported as SAEs:

- Development of a confirmed positive inhibitor (>0.6 BU) during the tapering or follow-up periods
- A patient develops a Grade 2 or greater allergic reaction in association with administration of rFVIIIFc defined as follows using the Recommendations for Grading of Acute and Subacute Toxic Effects on the WHO scale [[WHO Handbook 1979](#)] [40]:
  - Grade 2: bronchospasm; no parenteral therapy needed
  - Grade 3: bronchospasm; parenteral therapy required
  - Grade 4: anaphylaxis

Allergic reactions, including anaphylaxis, have been reported with FVIII products. The patients/caregivers should be informed of early symptoms and signs of hypersensitivity reactions, including difficulty breathing, chest tightness, swelling of the face, rash, or hives. If such an event occurs while the subject is at home, the patients/caregivers should be instructed to seek immediate medical care for the subject.

- A patient develops a vascular thrombotic event, with the exception of IV injection site thrombophlebitis

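### The end-of-treatment footnote in Protocol Table 2 (copied in SAP Table 3) equates developing an inhibitor with relapse, whereas Protocol 7.1.3 also requires a confirmed low incremental recovery

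*Protocol*

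**What the plan says.** Protocol 7.1.3, under Relapse, sets two conditions joined by AND: an inhibitor of at least 0.6 BU, and an IR of at most 66% of expected. Each must be found on two consecutive assessments within 2-4 weeks. If an assessment in tapering or follow-up suggests relapse, "the tests must be repeated at an unscheduled visit within 2 to 4 weeks to confirm relapse". Section 7.1.4 applies those criteria by reference: "A patient with confirmed relapse criteria will complete the end of treatment visit". After that visit, "No further investigational medicinal product will be provided".

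The schedule of events puts it differently. Footnote a, attached to the end of treatment visit column of Protocol Table 2 (Section 7.5.1.1), says: "Patients who develop inhibitors during the tapering or the follow-up period (i.e., who relapse) will proceed immediately to the end of treatment visit". SAP Section 12.1, Table 3, carries the same footnote.

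SAP 6.1.5.4 restates the two relapse conditions with AND between them, and SAP 6.3.13.2 uses that definition for the relapse proportion in the TPFAS.

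**The concern.** The footnote explains inhibitor development as relapse, as if the two were one event. Under 7.1.3 the inhibitor is only half of relapse. The schedule table is what site staff are likely to have open at a visit, and this footnote tells them when to end treatment. It gives no IR condition and no reference to 7.1.3.

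The patient at risk has a returned inhibitor but an IR still above 66% of expected. He has not relapsed as the protocol defines it and should stay on study. Such a patient is plausible: Protocol 7.1.2, writing of the ITI period, says that inhibitor levels commonly fluctuate. If he is sent out early, his study drug stops. The rest of his 48-week observation is lost for relapse, bleeding, missed days and hospitalizations. In a study of 20 patients, of whom only the ITI successes enter this period, each patient's follow-up counts.

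**Working it through.** No figure in the plan needs reproducing. The check applies each rule to one test patient and then bounds the follow-up he could lose.

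**Test patient:** ITI success; later an inhibitor of at least 0.6 BU on two assessments 2-4 weeks apart; IR above 66% of expected on both.

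- **Protocol 7.1.3:** first criterion met, second not met. Not a relapse; he stays.
- **Protocol 7.1.4:** exit follows confirmed relapse criteria, which he does not meet; he stays.
- **Protocol 7.5.6.1.1:** he has a reportable SAE, because the list includes "Development of a confirmed positive inhibitor (>0.6 BU) during the tapering or follow-up periods" with no IR condition. This is a reporting rule, not an exit rule. It also shows that the protocol recognises a confirmed inhibitor as an event separate from two-part relapse.
- **Protocol 7.3.3:** a confirmed inhibitor is not a listed withdrawal reason, although the investigator may withdraw a patient in his best interest.
- **Footnote a, opening words:** he has developed an inhibitor; he leaves at once.
- **Footnote a, parenthesis read as the defined term:** he has not relapsed; he stays.
- **SAP 6.1.5.4 and 6.3.13.2:** not counted as a relapse, but kept in the denominator.

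Only the opening words of footnote a remove him.

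**Does the parenthesis settle it?** Only partly. The protocol also uses the word relapse for titer alone: in Section 5.1.2 for a published case with a low-titer inhibitor, in Section 7.1.4 when giving the reason to maintain FVIII:C levels, and in Section 7.5.6.1.1 under lack of efficacy. The word therefore does not always lead a reader to the two-part definition.

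**Follow-up at stake.** Weeks lost = 48 - exit week, using the nominal visit weeks in Table 2.

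Exit at the visit itself (literal reading):
- Week 28: 48 - 28 = 20 weeks; 20/48 = 41.7%
- Week 40: 48 - 40 = 8 weeks; 8/48 = 16.7%

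Exit after a repeat test 2-4 weeks later (the interval is borrowed from 7.1.3):
- Week 28: 48 - 30 = 18 to 48 - 32 = 16 weeks; 37.5% to 33.3%
- Week 40: 48 - 42 = 6 to 48 - 44 = 4 weeks; 12.5% to 8.3%

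A first positive during tapering would cost more by the same formula. For example, exit at Week 16 loses 48 - 16 = 32 weeks (66.7%). All of these are ceilings, because a patient who later met both criteria would leave at that point anyway.

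**The case against.** The strongest reply is that footnote a is shorthand and not a rule of its own. Its parenthesis names relapse, a term defined with both conditions in the synopsis, Protocol 7.1.3 and SAP 6.1.5.4. Section 7.1.3 also makes repeat testing mandatory, in the plural, for both tapering and follow-up. This largely stands: the footnote is not a free-standing inhibitor-only stopping rule, and a site that reads the body text will act correctly. What it does not remove is that the footnote equates two things the protocol elsewhere keeps apart.

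Several stronger readings are tempting, and the documents do not support them:

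- **That the word immediately conflicts with the text.** It does not. The synopsis also sends relapsed patients directly to their final visit.
- **That the table leaves the repeat IR untaken.** Footnote f says "An unscheduled visit may be required to repeat inhibitor testing under this protocol" and does not mention IR, but it sits on the inhibitor-assay row, where that is natural. Section 7.1.3 requires the repeat tests, Section 7.1.6 allows unscheduled IR, and IR is drawn at every scheduled tapering and follow-up visit.
- **That exit is allowed only on two-part relapse.** Section 7.3.3 lets the investigator withdraw a patient on clinical judgment, and a confirmed inhibitor could prompt that under any footnote wording.
- **That the SAP adopts an either/or definition.** The lead-in of SAP 6.1.5.4 says *any* where *both* is meant, but the AND between the criteria makes the rule clear. This is a drafting slip.

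**Conclusion.** The wording is inconsistent in the current text of both documents, and the point is minor. Read literally, footnote a would end study drug and the remaining observation of a patient who has an inhibitor but has not relapsed.

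A reader might infer that each such patient shifts the reported relapse proportion by one over the number of ITI successes. That does not follow. SAP 6.3.13.2 counts relapse by the two-part definition, so a patient with preserved IR is not counted as relapsed. The listings of titer, IR and outcome in SAP 6.3.12 would show his status. He would instead count as relapse-free on a shortened observation, and no listing can restore the missing weeks.

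The size is therefore lost follow-up per affected patient, within the ceilings shown above. It rests on two assumptions: that a site follows the footnote without consulting 7.1.3, and that a patient with an inhibitor and preserved IR occurs. The documents give no frequency for either.

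**What to change.** In Protocol Table 2 and SAP Table 3, reword footnote a to: *Patients with confirmed relapse (both criteria in Protocol Section 7.1.3) will proceed to the end of treatment visit.* As an optional clean-up, change *any* to *both* in the lead-in of SAP 6.1.5.4.

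The protocol change is an amendment. Under Section 3.1, "It is the responsibility of the investigator to obtain approval of the study protocol, possible amendments" from the IEC/IRB, so it is best bundled with another amendment. The SAP changes need only a SAP revision. No sample, visit or analysis is added.

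The rewording protects only patients still in tapering or follow-up, and the SAP revision history places the current version just before database lock. If no patient remains in those periods, use the listings already planned in SAP 6.3.12 to see whether anyone left with an inhibitor and an IR above 66% of expected, and report his shortened follow-up next to the relapse proportion.
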